5.3. Randomisation Criteria

Those subjects who meet the randomisation criteria will be randomised into the study until the target of approximately 1020 randomised subjects is reached. At the end of the run-in period, study subjects must not meet any of the following criteria in order to be randomised to study treatment:

1. Pneumonia or moderate/severe COPD exacerbation during run-in
2. Any change to COPD maintenance medications (including dosage and regimen) during the run-in
3. Antibiotics for respiratory tract infections during the run-in

5.4. Screening/Baseline/Run-in Failures

A subject will be assigned a subject number at the time the informed consent is signed. A subject who is assigned a subject number but does not have Screening (V1) will be considered a pre-screen failure.

Screen failures are defined as subjects who consent to participate in the clinical trial but are never subsequently randomized. In order to ensure transparent reporting of screen failure subjects, meet the Consolidated Standards of Reporting Trials (CONSORT) publishing requirements, and respond to queries from Regulatory authorities, a minimal set of screen failure information is required including Demography, Screen Failure details, Eligibility Criteria, and Serious Adverse Events (see Section 7.4.2.5).

Subjects who are Pre-Screen (V0) or Screen (V1) failures cannot be re-screened.

5.5. Withdrawal/Stopping Criteria

5.5.1. Protocol defined withdrawal criteria

A subject must be permanently withdrawn if any of the following stopping criteria are met:

- **Liver Chemistry:** Meets any of the protocol-defined liver chemistry stopping criteria³ as defined in Section 5.5.2.
- **Pregnancy:** Positive urine pregnancy test.

The following actions must be taken in relation to a subject who fails to attend the clinic for a required study visit:

- The site must attempt to contact the subject and re-schedule the missed visit as soon as possible.
- The site must counsel the subject on the importance of maintaining the assigned visit schedule and ascertain whether or not the subject wishes to and/or should continue in the study.
- In cases where the subject is deemed 'lost to follow up', the investigator or designee must make every effort to regain contact with the subject (where possible, 3 telephone calls and if necessary a certified letter to the subject's last known mailing address or local equivalent methods). These contact attempts should be documented in the subject's medical record.
- Should the subject continue to be unreachable, only then will he/she be considered to have withdrawn from the study with a primary reason of "Lost to Follow-up".

A subject may withdraw from study treatment at any time at his/her own request, or may be withdrawn at any time at the discretion of the investigator for safety, behavioural or administrative reasons. If a subject withdraws from the study, he/she may request destruction of any samples taken, and the investigator must document this in the site study records. Subjects who are withdrawn from the study will not be replaced.

[figure not shown]
5.5.2. Liver Chemistry Stopping Criteria

Liver chemistry stopping and increased monitoring criteria have been designed to assure subject safety and evaluate liver event etiology (in alignment with the FDA premarketing clinical liver safety guidance).

<http://www.fda.gov/downloads/Drugs/GuidanceComplianceRegulatoryInformation/Guidances/UCM174090.pdf>

[figure not shown]
³ Based on findings from any routine labs done at site

Phase III-IV Liver Chemistry Stopping and Increased Monitoring Algorithm

Liver Safety Required Actions and Follow up Assessments Section can be found in [Appendix 2, Section 12.2](#)

Phase III-IV Liver Chemistry Increased Monitoring Algorithm with Continued Therapy for ALT ≥ 3xULN but < 8xULN

Liver Safety Required Actions and Follow up Assessments Section can be found in [Appendix 2](#), Section 12.2.

5.6. Subject and Study Completion

A completed subject is one who has completed all phases of the study including the follow-up phone-call or visit.

The end of the study is defined as the last subject's last visit.

6. STUDY TREATMENT

6.1. Investigational Product and Other Study Treatment

The term 'study treatment' is used throughout the protocol to describe any combination of products received by the subject as per the protocol design. Study treatment may therefore refer to the individual study treatments or the combination of those study treatments.

All treatments will be delivered by ELLIPTA containing 30 doses.

Following the run-in period, eligible subjects will be randomized (1:1) to one of the following double-blind treatment groups:

- FF/UMEC/VI 100mcg/62.5mcg/25mcg and placebo, both via the ELLIPTA once daily in the morning
or,
- FF/VI 100mcg/25mcg and UMEC 62.5mcg, both via the ELLIPTA once daily in the morning.

The randomisation will be stratified based on long-acting bronchodilator usage during the run-in (none, one or two long-acting bronchodilators per day).

The ELLIPTA contains 30 doses (FF/UMEC/VI, FF/VI, UMEC or placebo). Each subject will be instructed on the proper use of the ELLIPTA and will inhale once from each of their ELLIPTAs each morning for the duration of the 24-week treatment period. Subjects will self-administer their first dose of blinded study treatment in the clinic during Randomisation (V2). On the morning of the other study clinic visits, subjects will refrain from taking their morning dose of study treatment until instructed to do so by clinic personnel. Subjects will take their last dose of study treatment at the clinic at Visit 5 and a safety follow-up will be conducted either by phone call or clinic visit approximately one week later. Subjects will discontinue their existing COPD medication on the day before Randomisation (V2) but may continue their study-supplied rescue albuterol/salbutamol.

There are no plans to provide the study drug for compassionate use following study completion.

Descriptions of the study treatments administered via the ELLIPTA are provided in [Table 2](#).

Table 2 Description of study treatment inhalation powder via ELLIPTA

FF/UMEC/VI	First strip	Second strip
		FF blended with lactose
Dosage Form	ELLIPTA with 30 doses (2 strips with 30 blisters per strip)	
Unit Dose Strengths	100mcg per blister	62.5 mcg per blister UMEC, 25 mcg per blister VI
Physical description	Dry white powder	Dry white powder
Route of Administration	Inhaled	
FF/VI	First strip	Second strip
	FF blended with lactose	VI blended with lactose and magnesium stearate
Dosage Form	ELLIPTA with 30 doses (2 strips with 30 blisters per strip)	
Unit Dose Strengths	100mcg per blister	25 mcg per blister
Physical description	Dry white powder	Dry white powder
Route of Administration	Inhaled	
UMEC	First strip	Second strip
	UMEC blended with lactose and magnesium stearate	NA – one strip only
Dosage Form	ELLIPTA with 30 doses (1 strip with 30 blisters)	
Unit Dose Strengths	62.5 mcg per blister	NA
Physical description	Dry white powder	NA
Route of Administration	Inhaled	
Placebo to match	First strip	Second strip
	Lactose	NA – one strip only
Dosage Form	ELLIPTA with 30 doses (1 strip with 30 blisters)	
Unit Dose Strengths	NA	NA
Physical description	Dry white powder	NA
Route of Administration	Inhaled	

Albuterol/salbutamol via metered-dose inhaler (MDI) with a spacer will be issued for reversibility testing at Screening (V1). Albuterol/salbutamol MDI or NEBULES™ for as needed (prn) use throughout the study will be provided starting at Screening (V1). Albuterol/salbutamol and spacers will be sourced from local commercial stock. If not available locally, GSK will source centrally.

6.1.1. Storage

All study treatment should be stored up to 25°C (77°F). Each ELLIPTA contains 30 doses and is packaged in a foil pouch with a desiccant sachet and stored in a carton. The inhaler should not be used for more than 30 days after opening the foil. The sites must maintain a daily temperature log for the storage of investigational product.

Investigational product must be stored in a secure area under the appropriate physical conditions for the product. Access to and administration of the investigational product will be limited to the investigator and authorized site staff. Details of study treatment administration oversight are provided in the Study Procedures Manual (SPM). Investigational product must be dispensed or administered only to subjects enrolled in the study and in accordance with the protocol.

6.1.2. Investigational Product and albuterol/salbutamol Return

All used and unused study treatment and albuterol/salbutamol will be returned to GSK at the end of the study to be available for disposal. In some instances for sites outside the US, study supplies will be disposed of locally either by the site, the country medical department or third-party vendor. Detailed instructions for the return of the study drug can be found in the SPM.

If any ELLIPTA fails to function properly, the subject should return to the clinic as soon as possible to obtain a new inhaler. The site will use the interactive response technology (IRT) system to obtain a new treatment pack number for the subject and dispense a new study treatment kit from the site's investigational product supply as instructed by the IRT system.

In addition, any ELLIPTA or metered-dose-inhaler (MDI) that fails to function properly must be identified and returned to GSK for testing. Details of the failure will be documented in the eCRF.

6.2. Medical Devices

Medical devices (not manufactured by or for GSK) provided for use in this study are spacers/holding chambers.

Instructions for medical device use are provided in the SPM.

6.3. Treatment Assignment

Subjects will be assigned to study treatment in accordance with the randomisation schedule. The randomisation code will be generated by GSK using a validated computerized system. Subjects will be randomized using an IRT System, RAMOS NG. The study will use country based randomisation to allocate treatments. Once a randomisation number is assigned to a subject it cannot be reassigned to any other subject in the study.

Subjects who meet the eligibility criteria and successfully complete the 2-week run-in period will be randomized (1:1) to one of the following study treatment regimens:

- FF/UMEC/VI 100mcg/62.5mcg/25mcg and placebo, both via the ELLIPTA once daily in the morning
- or,
- FF/VI 100mcg/25mcg and UMEC 62.5mcg, both via the ELLIPTA once daily in the morning.

The randomization will be stratified based on **long-acting bronchodilator** usage during the run-in (none, one or two **long-acting bronchodilators** per day).

Subjects will be instructed to take one dose each morning from each ELLIPTA.

The duration of treatment for each subject is 24 weeks. On the morning of each clinic study visit, subjects will refrain from taking their morning dose of study treatment until instructed to do so by clinic personnel. Study treatment will be given at the clinic at approximately the same time of day as Randomisation (V2). On the other days during the treatment period (*i.e.* “non-clinic days”), subjects will be instructed to take their study treatment each morning at approximately the same time of day. The IRT system will provide a means for site-based allocation of drug. Each investigator will be supplied with sufficient supplies to conduct the trial. Additional treatment packs will be supplied as needed to the sites. Details of how to use the IRT system to randomize subjects is provided in the SPM.

6.4. Blinding

This will be double-blind study (with a placebo ELLIPTA used to maintain the blind) and the following will apply.

- The investigator or treating physician may unblind a subject’s treatment assignment **only in the case of an emergency** OR in the event of a serious medical condition when knowledge of the study treatment is essential for the appropriate clinical management or welfare of the subject as judged by the investigator.
- Investigators have direct access to the subject’s individual study treatment.

- It is preferred (but not required) that the investigator first contacts the Medical Monitor or appropriate GSK study personnel to discuss options **before** unblinding the subject's treatment assignment.
- If GSK personnel are not contacted before the unblinding, the investigator must notify GSK as soon as possible after unblinding, but without revealing the treatment assignment of the unblinded subject, unless that information is important for the safety of subjects currently in the study.
- The date and reason for the unblinding must be fully documented in the eCRF

A subject will be withdrawn if the subject's treatment code is unblinded by the investigator or treating physician. The primary reason for discontinuation (the event or condition which led to the unblinding) will be recorded in the eCRF.

- GSK's Global Clinical Safety and Pharmacovigilance (GCSP) staff may unblind the treatment assignment for any subject with an SAE. If the SAE requires that an expedited regulatory report be sent to one or more regulatory agencies, a copy of the report, identifying the subject's treatment assignment, may be sent to investigators in accordance with local regulations and/or GSK policy. Subjects will not be withdrawn from the study.

6.5. Packaging and Labeling

The contents of the label will be in accordance with all applicable regulatory requirements.

6.6. Preparation/Handling/Storage/Accountability

No special preparation of study treatment is required.

- Only subjects enrolled in the study may receive study treatment and only authorized site staff may supply study treatment. All study treatments must be stored in a secure environmentally controlled and monitored (manual or automated) area in accordance with the labelled storage conditions with access limited to the investigator and authorized site staff.
- The investigator, institution, or the head of the medical institution (where applicable) is responsible for study treatment accountability, reconciliation, and record maintenance (i.e. receipt, reconciliation and final disposition records).
- Further guidance and information for final disposition of unused study treatment are provided in the SPM.
- Under normal conditions of handling and administration, study treatment is not expected to pose significant safety risks to site staff. Take adequate precautions to avoid direct eye or skin contact and the generation of aerosols or mists. In the case of unintentional occupational exposure notify the monitor, Medical Monitor and/or GSK study contact.

- A Material Safety Data Sheet (MSDS)/equivalent document describing occupational hazards and recommended handling precautions either will be provided to the investigator, where this is required by local laws, or is available upon request from GSK.

6.7. Compliance with Study Treatment Administration

When subjects are dosed at the site, they will receive study treatment under medical supervision. The date and time of each dose administered in the clinic will be recorded in the source documents. The dose of study treatment and study subject identification will be confirmed at the time of dosing by a member of the study site staff. When subjects self-administer study treatment at home, compliance with study treatment will be assessed through querying the subject during the site visits and recording the number of doses remaining in the ELLIPTA in the eCRF. A record of the number of ELLIPTAs dispensed to each subject must be maintained and reconciled with study treatment and compliance records. Treatment start and stop dates will also be recorded in the eCRF. Study treatment non-compliance is defined as <80% or >120% over the 24-week treatment period.

6.8. Treatment of Study Treatment Overdose

An overdose is defined as a dose greater than the total doses described above which results in clinical signs and symptoms. These should be recorded by the investigator on the AE/SAE pages. In the event of an overdose of study treatment, the investigator should use clinical judgment in treating the overdose and contact the GSK medical monitor.

GSK is not recommending specific treatment guidelines for overdose and toxicity management. The investigator is advised to refer to the relevant document(s) for detailed information regarding warnings, precautions, contraindications, adverse events, and other significant data pertaining to the study drug being used in this study. Such documents may include, but not be limited to, the IB or equivalent document provided by GSK.

6.9. Treatment after the End of the Study

Subjects will not receive any additional treatment from GSK after completion of the study because other treatment options are available.

The investigator is responsible for ensuring that consideration has been given to the post-study care of the subject's medical condition, whether or not GSK is providing specific post-study treatment.

6.10. Concomitant Medications and Non-Drug Therapies

All COPD medications used within approximately 3 months prior to Screening (V1) and during the study (including the post-treatment period) should be recorded in the eCRF.

All non-COPD medications taken during the study (after randomisation including post-treatment) and any changes to concomitant medications will be recorded in the eCRF. [Note: Study provided albuterol/salbutamol should not be recorded in the eCRF however non-study supplied albuterol/salbutamol will be recorded in the eCRF]. The minimum requirement is that drug name, dose, route and the dates of administration are to be recorded.

Medications initiated after completion of the randomized treatment phase of the study (V5) or started after withdrawal from the study must be recorded in the eCRF, along with any changes up to the Safety Follow-Up Visit/Phone-call.

6.10.1. Permitted Medications and Non-Drug Therapies

- The following COPD medications are permitted during the study treatment period:
- Study supplied albuterol/salbutamol MDI or Nebules (must be withheld for at least 4 hours prior to spirometry testing).
- Oral or injectable corticosteroids (short course ≤ 14 days) only for the short term treatment of COPD exacerbations and/or pneumonia.
- Antibiotics (short course ≤ 14 days) for the short term treatment of COPD exacerbations and/or pneumonia.
- Mucolytics such as acetylcysteine.
- Long term oxygen therapy. (To be eligible to enter the study subjects who are on LTOT must be using at a flow rate of ≤ 3 litres/minute at rest. However, oxygen therapy may be adjusted as deemed medically necessary at any time during the study.) Oxygen therapy must be captured on the concomitant medication page of the eCRF. Supplemental oxygen is recommended for patients who exhibit oxyhemoglobin desaturation with rest or exertion (e.g. SaO₂ $\leq 88\%$).
- Maintenance phase of pulmonary rehabilitation treatment (subjects are not allowed to initiate treatment during the study).
- Any COPD medication deemed medically necessary for the short term treatment (≤ 14 days) of a moderate/severe COPD exacerbation or pneumonia.

The following relevant **Non-COPD medications** are permitted during the study:

- Medications for rhinitis (e.g. intranasal corticosteroids, antihistamines, cromolyn, nedocromil, nasal decongestants).
- Topical and ophthalmic corticosteroids.
- Localized corticosteroid injections (e.g. intra-spinal and intra-articular).
- Vaccinations (Influenza vaccine, Pneumonia vaccine, Shingles vaccine, etc.) (Administration of influenza and pneumonia vaccines should be considered based on clinical discretion of the Investigator and local/national guidelines. Current

influenza vaccines and pneumonia vaccines will be captured on the concomitant medication pages of the eCRF).

- Allergy immunotherapy.
- Antibiotics for short-term treatment (≤ 14 days) of acute infections. (Long term treatment with antibiotics is not allowed).
- Systemic and ophthalmic beta-blockers. (Administer with caution as systemic beta-blockers block the pulmonary effect of beta-agonists, and may produce severe bronchospasm in patients with reversible obstructive airways disease. Cardioselective beta-blockers should be considered, although they also should be administered with caution).
- Smoking cessation treatments.
- Cough suppressants.
- Tricyclic antidepressants and monoamine oxidase inhibitors (MAOIs). (Administer with extreme caution as they may potentiate the effects of beta-agonists on the cardiovascular system, including QTc prolongation).
- Diuretics. (Caution is advised in the co-administration of beta-agonists with non-potassium sparing diuretics as this may result in ECG changes and/or hypokalaemia).
- Use of positive airway pressure for sleep apnoea.
- Oral muscarinic antagonists for the treatment of overactive bladder are permitted but should be used with caution as they may exacerbate medical conditions that are contraindicated for anticholinergics (e.g., narrow angle glaucoma and bladder outflow obstruction).
- CYP3A4 inhibitors (Caution should be exercised when considering the coadministration of long-term ketoconazole and other known strong CYP3A4 inhibitors (e.g., ritonavir, clarithromycin, conivaptan, indinavir, itraconazole, lopinavir, nefazodone, nelfinavir, saquinavir, telithromycin, troleandomycin, voriconazole) because increased systemic corticosteroid and increased cardiovascular adverse effects may occur).

6.10.2. Prohibited Medications and Non-Drug Therapies

Medications prohibited at specific time intervals prior to Visit 1 (and at any time during the study) are identified in the Exclusion Criteria (Section 5.2).

NOTE: All COPD medications (except for rescue albuterol/salbutamol, mucolytics and oxygen) are prohibited during the randomised period of the study except during the treatment of a moderate/severe COPD exacerbation or pneumonia. In the event of an exacerbation or pneumonia, sites should attempt to follow protocol treatment guidelines (Section 12.7); however, treatment with any medication that the health care provider deems necessary is allowed. Caution is advised in using a LABA or LAMA to treat a subject currently taking study treatment as these additional medications may increase the risk of overdose. If necessary the investigator or other health care personnel may stop the

subjects study treatment temporarily in order to treat the COPD exacerbation. Subjects who require more than two consecutive 14 day courses of treatment (i.e. antibiotics or corticosteroids) should be evaluated for their continuation on study treatment by the investigator in consultation with the GSK medical monitor.

Eligible subjects will be allowed to continue their usual COPD medications during screening and the 2-week run-in period. On the morning of the Screening Visit subjects will refrain from taking their morning dose of their usual COPD medications until instructed to do so by clinic personnel. During the run-in period subjects will continue to use their usual COPD medications with no change in medication or dose.

The number of long-acting bronchodilators taken each day during the run-in period (0, 1 or 2) will be recorded.

On the day before the Randomisation Visit (V2), subjects will take their last dose of their usual COPD medications and will not use any other COPD medications (except for those allowed per protocol: rescue albuterol, oxygen, mucolytics and medications for the treatment of a COPD exacerbation or pneumonia) until the end of the study. Rescue albuterol/salbutamol can be used throughout the study as needed but must be withheld for at least 4 hours prior to conducting spirometry.

COPD Medications and non-drug therapies that are prohibited during the randomized portion of the study:

- Inhaled and systemic corticosteroids (Except for the short term treatment [≤ 14 days] of a COPD exacerbation or pneumonia.) **Note:** Topical and ophthalmic corticosteroids, and localized corticosteroid injections (intra-spinal and intra-articular) are allowed.
- Long and short acting muscarinic antagonists
- Long and short acting β_2 -agonists
- PDE4 inhibitors (roflumilast)
- Theophylline preparations
- Cromoglycate and nedocromil inhalers
- Zafirlukast, montelukast, zileuton
- Acute phase of pulmonary rehabilitation (at any time during the study including run-in)
- Long term systemic antibiotic therapy (antibiotics used for ≤ 14 days are allowed)

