4.2. Treatment Arms and Duration

Subjects who meet all the inclusion/exclusion criteria and who have successfully completed all protocol procedures at Screening (V1) will enter the two-week run-in period. Following the run-in period, eligible subjects will be randomised (1:1) to one of the following double-blind treatment groups for 24-weeks.

- FF/UMEC/VI 100mcg/62.5mcg/25mcg and placebo, both via the ELLIPTA once daily in the morning.
- or,*
- FF/VI 100mcg/25mcg and UMEC 62.5mcg, both via the ELLIPTA once daily in the morning.

The ELLIPTA contains 30 doses (FF/UMEC/VI, FF/VI, UMEC or placebo) and subjects will be instructed to administer one dose from each ELLIPTA once daily in the morning.

The randomisation will be stratified based on **long-acting bronchodilator** usage during the run-in (none, one or two **long-acting bronchodilators** per day).

The total duration of subject participation will be approximately 27 weeks, consisting of a 2-week run-in period, 24-week treatment period and a 1-week follow-up period.

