10.1.2. Exclusions from mPP Population

The full list of protocol deviations collected on the eCRF is in the PDMP.

The mPP Population is the primary analysis population, comprising all subjects from ITT population with the exception of:

- Full exclusion: subjects who have a full protocol deviation considered to impact primary endpoint (trough FEV1)
 - Eligibility criteria (those that impacts primary endpoint as listed in PDMP, [Appendix 2](#)) not met
 - Treatment non-compliance (overall compliance <80% or >120% over the 24-week treatment period, based on active treatment)
 - Randomisation criteria not met
 - Pneumonia or moderate/severe COPD exacerbation during run-in
 - Any change to COPD maintenance medications (including dosage and regimen) during the run-in
 - Antibiotics for respiratory tract infections during the run-in
- Partial exclusion: subjects who have a protocol deviation considered to impact primary endpoint. Trough FEV1 assessments collected after the incidence of the protocol deviation will be excluded from primary analysis.
 - Subject received incorrect container which contains incorrect study treatment.
 - Subjects took prohibited medication during treatment period, as detailed in PDMP [Appendix 3](#) Prohibited Medication.

- Partial exclusion: other events (not a protocol deviation) considered to impact the primary endpoint. Trough FEV1 assessments collected on or after the event start date will be excluded from primary analysis.
 - Subjects had a moderate/severe COPD exacerbation
 - Subjects had pneumonia.
 - Subjects who were unblinded by GCSP due to safety concerns.

Note: Subjects who received incorrect treatment and non-compliance based on active treatment will be identified as important PDs and flagged as PP exclusionary following treatment unblinding. These PDs will be flagged as PP exclusionary in ADaM DV dataset and will be included in summary of exclusion from mPP population table.

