1.34.	ITT	Summary of On-Treatment COPD Concomitant Medications, Medications Given for Reasons other than an Exacerbation	SAC
1.35.	ITT	Summary of Post-Treatment COPD Concomitant Medications, Medications Given for Reasons other than an Exacerbation	SAC
1.36.	ITT	Summary of Concomitant Medications Taken in the Run-in Given for An Exacerbation	SAC
1.37.	ITT	Summary of On-Treatment Concomitant Medications Given for an Exacerbation	SAC
1.38.	ITT	Summary of Post-Treatment Concomitant Medications Given For an Exacerbation	SAC
1.39.	ITT	Summary of On-Treatment Non-COPD Concomitant Medications	SAC
1.40.	ITT	Summary of Post-Treatment Non-COPD Concomitant Medications	SAC
Treatment Compliance			
1.41.	ITT	Summary of Treatment Compliance (%)	SAC

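### Protocol 6.10.2 gives the ban on usual COPD medication two end points, one of which runs past Visit 5 into the follow-up week

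*Protocol*

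**What the plan says.** Protocol 6.10.2 states the ban on COPD medication three times.

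- The NOTE says that, apart from rescue, mucolytics and oxygen, COPD medications "are prohibited during the randomised period of the study except during the treatment of a moderate/severe COPD exacerbation or pneumonia".
- The heading of the list reads "COPD Medications and non-drug therapies that are prohibited during the randomized portion of the study".
- The paragraph on the day before Visit 2 (V2) tells subjects to take their last usual dose and then use no other COPD medication, with exceptions that close with "medications for the treatment of a COPD exacerbation or pneumonia) until the end of the study".

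On what the study covers, Section 4.2 describes participation as "consisting of a 2-week run-in period, 24-week treatment period and a 1-week follow-up period". Section 5.6 says "A completed subject is one who has completed all phases of the study including the follow-up phone-call or visit", and separately sets the end of the study at the final visit of the final subject.

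On the period after Visit 5 (V5), Section 6.10 says "Medications initiated after completion of the randomized treatment phase of the study (V5) or started after withdrawal from the study must be recorded", up to the follow-up contact. Section 6.10.1 lists permitted COPD medications for the study treatment period. SAP 10.1.2 makes it a partial exclusion when "Subjects took prohibited medication during treatment period". SAP Table 1.35 is titled "Summary of Post-Treatment COPD Concomitant Medications, Medications Given for Reasons other than an Exacerbation".

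**The concern.** Two of the three statements stop the ban with randomised treatment. The third carries it to a later point. It is also the sentence that tells site and subject what to do with usual medication, so it is an operative instruction and not background text. Section 7 allows no waivers except for immediate safety concerns, so a site should not have to choose between two written end points.

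At stake is maintenance treatment for subjects with advanced (GOLD Group D) COPD in the week after V5. Study treatment has ended by then, and on the longer reading usual maintenance could not restart until the follow-up contact.

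**Working it through.** **Plan's own figure.** Section 4.2 gives the phases as 2, 24 and 1 weeks: 2 + 24 + 1 = 27 weeks, which matches the stated total of about 27. The follow-up week is part of participation but lies outside the 24-week treatment period.

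**When each version of the ban ends.**

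- *NOTE and list heading:* the randomised period. Section 6.10 places the end of the randomised treatment phase at V5.
- *V2 paragraph, subject-level reading of 5.6:* the follow-up contact, because a subject is complete only after it.
- *V2 paragraph, formal definition in 5.6:* the last visit in the whole trial. For most subjects this is later still, and it cannot sensibly govern one person's medication.

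Both protocol definitions therefore put the end of the ban after V5.

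**Which end was intended.** Section 6.10 has medications begun after V5 or withdrawal recorded, not barred. Section 6.10.1 uses the treatment period as its window. SAP 10.1.2 counts prohibited medication only in that period. SAP Table 1.35 expects COPD medication after treatment for reasons other than an exacerbation. All four point to V5 or Early Withdrawal.

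**Size of the gap on the subject-level reading, for a completer.** Inputs: last study dose in clinic at V5 (Section 6.1); once-daily dosing; follow-up contact one week later with a window of -1/+4 days (Section 7.1).

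- Days from V5 to contact: nominal 7; earliest 7 - 1 = 6; latest 7 + 4 = 11.
- The V5 dose covers that day. If maintenance restarts on the day of contact, missed daily doses are 7 - 1 = 6, with range 6 - 1 = 5 to 11 - 1 = 10.
- On the intended reading the ban itself causes no missed dose.

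For early withdrawals the same count runs from the Early Withdrawal Visit if a dose is taken there. Any gap before that visit is not given in the documents.

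**Rescue supply.** The Time and Events Table dispenses albuterol at Visits 1 to 4 and collects it at V5 and Early Withdrawal. Rescue use stays allowed in the follow-up week, but no study supply is scheduled for it.

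**Effect on analyses.** Trough FEV1 is last measured before the V5 dose, and the V5 questionnaires precede dosing as well. Time to first exacerbation is censored at treatment stop + 1 day (SAP 10.6.4), so it reaches at most the first day without a dose, under the same rule in both arms. The planned tables titled as post-treatment that bear on this interval are 1.35 and 1.38 (medication), 2.19 (exacerbations) and 3.5, 3.24, 3.25, 3.27 and 3.29 (safety): 2 + 1 + 5 = 8. SAP Table 5 also plans a post-treatment SAE summary. All are descriptive. Table 1.40 covers non-COPD medication, which this ban does not govern.

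**The case against.** The best defence is that a sensible site would read the sentence as ending at V5. The next sentence in 6.10.2 allows rescue albuterol for the whole study, yet that supply is collected at V5, so in this paragraph the study seems in practice to stop there. SAP 10.6.1 counts a subject as having completed the study at Visit 5. Section 6.9 makes the investigator responsible for considering later care. No document shows a site withholding maintenance after V5.

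Much of this stands as evidence of intent, and it is why the point is minor. It does not remove the conflict. SAP 10.6.1 is contradicted by SAP 10.7.1, which includes the safety follow-up in completion, and the SAP does not instruct sites on medication. Section 6.9 takes effect on completion of the study, so it does not settle the date.

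A reader might also infer that the protocol deliberately leaves subjects untreated for a week, that they have no relief medication, or that the trial's results are affected. The documents support none of these. The other provisions show the ban was meant to end at V5 or Early Withdrawal. Rescue use and treatment of an exacerbation or pneumonia remain allowed throughout. No efficacy model rests on the follow-up week.

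**Conclusion.** The inconsistency is real and sits in current protocol text. One sentence in 6.10.2 carries the ban past V5, while the rest of that section and the related provisions end it with randomised treatment. On the subject-level reading a completer would miss about 6 daily maintenance doses (5 to 10); on the intended reading, none. The count assumes that the V5 dose is taken, that dosing is counted once daily, and that maintenance would restart on the day of the follow-up contact. Whether any site would act on the longer reading is not known from the documents.

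Severity is minor and limited to patient care. Sample size, analysis populations and efficacy analyses do not change. Only the descriptive post-treatment summaries of COPD medication, exacerbations and safety cover the interval.

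**What to change.** In Protocol 6.10.2, change the closing words of the V2 paragraph so that the ban runs *until completion of Visit 5 or the Early Withdrawal Visit*, and add that COPD treatment after that visit is at the investigator's discretion, consistent with Section 6.9.

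In the same pass, check the other bans worded by reference to the study as a whole, and decide whether each should end at the same visit: the opening line of 6.10.2 on medications excluded under Section 5.2; the bar in 6.10.1 on starting pulmonary rehabilitation; and the acute-phase rehabilitation item in the 6.10.2 list.

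The cost is one phrase and a short check, carried in the next protocol amendment and the separate South Korea version, with ethics review as applicable. Amendment 3 was itself issued for minor clarifications of this kind. No SAP change and no extra subjects, visits or analyses are needed. The benefit reaches only subjects who have not yet passed their follow-up contact.
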